PQXNIH2- Protocol & Data and Safety Monitoring Plan

NCT04585451

By [name] and [name]

PQXNIH2- Protocol & Data and Safety Monitoring Plan

Study Overview

PainQx is currently engaged in the second phase of a two phase NIDA sponsored project entitled “Development of a Clinical Tool Utilizing an EEG-Based Algorithm for the Objective Quantification of Pain” funded under FOA Number PA-16-302 Omnibus Solicitation of the NIH, CDC, FDA, and ACF for Small Business Innovation Research Grant Applications (Parent SBIR [R43/R44]).

In Phase I of the project, PainQx demonstrated that 19 lead EEG data can be used to detect changes in brain activity when a patient is in pain and produced a biomarker that scales with the intensity of chronic pain the patient is reporting via the Numeric Rating Scale (NRS) 0-10 scale.

The primary purpose of this study is to demonstrate that the relationship between the NRS and a QEEG based biomarker demonstrated using 19 lead research oriented EEG systems can be replicated using a lower cost, portable EEG recording device that can be set up quickly by a non-specialist thereby significantly improving clinical utility of the ALGOS platform. The targeted EEG recording device for use in the study will also be used for the FDA Validation Trial and initial commercial product launch, thus this study will serve as an FDA Beta in addition to supporting achievement of the NIDA Phase II objectives.

Phase II Research Strategy

Phase II Hypothesis

The relationship between the NRS and a QEEG based biomarker demonstrated using 19 leads can be demonstrated using a commercially available EEG recording device that can be set up by a non-specialist in less than 10 minutes, thereby significantly improving clinical utility.

Specific Aim 1

Select an EEG recording device and transition the developed software modules to work with the selected EEG recording device.

Specific Aim 2

Optimize the PainQx algorithm and demonstrate performance using the selected EEG recording device from Phase II Specific Aim 1.

Power Analysis

The performance achieved as part of Phase I of the NIDA study was used to estimate the minimum number of subjects required for Phase II. Because of the potential for performance degradation and/or the need to perform statistical analysis on subsets of the data (e.g. performance for each pain etiology included in the study, additional enrollment is planned beyond the minimum number of subjects indicated by the power analysis.

PQXNIH2- Protocol & Data and Safety Monitoring Plan

Inclusion and Exclusion Criteria

Subjects

Two hundred fifty (250) male and female pain patients with symptoms in excess of 3 months duration (per the IASP definition of Chronic Pain) between the ages of 18-85 years will be enrolled in this phase of the study. Fifty (50) healthy normal subjects between the ages of 18-85 years will also be enrolled. The normal subjects are added to assure that the study spans the entire pain scale including those with an NRS of 0. Subjects who meet inclusion/exclusion criteria will be asked to volunteer for the study and to provide written informed consent. Subjects will receive a fee for participation to reimburse them in part for their travel and time.

Defining Chronic Pain (CP)

For this study, we will apply the guidelines of the International Association for the Study of Pain (IASP). IASP defines chronic pain as “pain which has persisted beyond normal tissue healing time, taken, in the absence of other criteria, to be 3 months or greater”. The IASP definition is most widely applied in published studies, although it is noted that severity, disability, and impact on daily life and mood are not considered in this definition. Therefore, to supplement the IASP guidelines, we have added measures of each of these dimensions in the clinical self-report forms to further characterize patients within the group (see below).

Inclusion Criteria, Pain Patients

- Male and female chronic pain patients
- Patients between the ages of 18-85 years
- Patients exhibiting the presence of symptoms in excess of 3 months duration
- Patients suffering from neuropathic (e.g., lower back pain), osteoarthritis, or muscular skeletal pain
- Patients with evidence of pathology related to the painful condition on which diagnosis was made (e.g., results of imaging or diagnostic pain code)
- Patients with NRS pain scores across the full range (1-10) at the time of testing

Inclusion Criteria, Normal (no-pain) Group

- Subjects will be included with no history of pain with a duration of greater than 3 months, and no report of pain at the time of testing (or within 3 months of testing)

PQXNIH2- Protocol & Data and Safety Monitoring Plan

Exclusion Criteria

- Patients with medically diagnosed psychotic illness
- Patients with medically diagnosed drug or alcohol dependence in the past 12 months
- Patients with a medical history of head injury with loss of consciousness and amnesia (within the last 2 years)
- Patients with skull abnormalities that preclude the proper placement of the electrodes for the EEG data acquisition
- Patients who have a spinal cord stimulator, or other implantable devices
- Patients for whom the source of pain at the time of the evaluation is associated with: neurological disorders (multiple sclerosis, Parkinson, dementia), diabetes, migraines, or those with reflex / sympathetic dystrophy disorder/complex regional pain syndrome, fibromyalgia, or visceral pain

Note: This does not exclude patients who suffer from these disorders if the current source of pain is not due to the disorder. For example, patients with diabetes are NOT excluded, but patients whose pain at the time of the evaluation is a result of diabetic neuropathy are excluded. Similarly, patients with a history of migraines but for whom a migraine is not the current source of pain at the time of the evaluation are NOT excluded.

- Patients with cancer
- Patients on workers compensation or disability
- Patient on anticonvulsant medication
- Patients who have a history of seizures

All patients meeting inclusion/exclusion criteria and who provide written informed consent will be enrolled in the study.

Analgesic medication prescribed for a candidate patient's pain condition will be allowed in the following categories: oral and transcutaneous narcotics, tricyclic antidepressants, SNRIs, anticonvulsants, non-steriodals, and corticosteroids.

PQXNIH2- Protocol & Data and Safety Monitoring Plan

Trial Management

Target Population Distribution

While both genders will be sampled, the sample will be a convenience sample of patients present to the offices of the referring physicians. There are no plans to control for gender, but the convenience nature may impact gender balance of the sample. It is expected that gender will be approximately 50-50 in this sample.

Likewise, it is expected that race and ethnicity will be proportional to the reported incidence of chronic pain within the patient population of the practices and programs from which the subjects were referred. The quantitative EEG methods that will be used in this study and the location and activation of brain regions of interest in a chronic pain state have been determined to be culture, ethnic and gender neutral, so strict control of these study variables is not considered a requirement.

Data Management & Analysis

Data Acquisition

Equipment & EEG Acquisition

For the initial 100 participants, PainQx will be providing one or more EEG headsets and EEG data collection devices from BioSignal Group to be used to collect subject neural activity. Following the initial collection period, PainQx will provide EEG headsets and collection devices from Zeto, Inc.

Fifteen (15) minutes of eyes-closed resting EEG will be recorded with the device placed in accordance with the International 10/20 Electrode Placement System, referenced to linked earlobes. In this phase of the study, the 15 minutes of EEG data collected will be divided into two segments with the first 10 minutes used to extract 2 minutes of artifact-free data, and the additional 5 minutes of data used for demonstration of replicability. ECG data will also be collected during the period of acquisition using the Zeto, Inc device. Patients will be monitored for vigilance during EEG and ECG recording.

- i. All electrode impedances will be below 10,000 Ohms.
- ii. The EEG amplifiers will have a bandpass from 0.5 to 80 Hz (3 dB points), with a 60 Hz notch filter. Data will be sampled at a rate of 500 samples/sec with 24-bit resolution.
- iii. Patients will be monitored for vigilance during EEG recording.

Collection of Subject Self-Rating and Pain Scales

The following self-rating scales will be used to provide critical data on severity, disability, mood, and neuropathy, as well as relevant patient history. It is recommended that the patient survey information be collected as the EEG is being set up on the patient to reduce the total time required

PQXNIH2- Protocol & Data and Safety Monitoring Plan

for the clinical study. A brief training video will be shown to the patient before the survey begins. This video describes the test, good practices during the test, and description of NRS.

- i. [Brief Pain Inventory \(BPI\)](#): This is used to rate overall pain, current pain and maximal pain over varied time periods and to indicate regions of pain. The form was developed by the Pain Research Group of WHO Collaborating Centre for Symptom Evaluation in Cancer Care. Also included are the influence of pain on activities of daily life, quality of life and current medications.
- ii. [Oswestry Disability Questionnaire](#): Used to quantify information about how the patient's pain affects their ability to manage everyday life.
- iii. [Neuropathic Pain Questionnaire](#): This validated scale rates the presence or absence of neuropathic pain.
- iv. [PROMIS - Depression](#): The PROMIS Depression instruments assess self-reported negative mood (sadness, guilt), views of self (self-criticism, worthlessness), and social cognition (loneliness, interpersonal alienation), as well as decreased positive affect and engagement (loss of interest, meaning, and purpose).
- v. [PROMIS - Anxiety](#): The PROMIS Anxiety instruments measure self-reported fear (fearfulness, panic), anxious misery (worry, dread), hyperarousal (tension, nervousness, restlessness), and somatic symptoms related to arousal (racing heart, dizziness)
- vi. [Clinical History and Treatment History](#): The referring physician will fill out a form containing clinical history, pertinent radiological and electrodiagnostic data and relevant clinical findings. Special attention will be paid to details of the treatment history, the time since onset of painful symptoms and medication history, including present medications.
- vii. The EEG technician will obtain a pain rating at the start and end of each EEG session using the 10-point Visual Analog Scale (VAS).

Data Entry Methods

PainQx will provide the clinical site with a tablet and access to an electronic case report form (ECRF) from Survey Analytics to facilitate easy input and analysis of clinical subject information. The ECRF will collect all the subject survey information, clinical, demographic, medication and symptom data.

Quality Assurance

To ensure the validity and integrity of the data PainQx will be conducting monthly data reviews. PainQx will focus on the quality of the EEG collected to ensure that features that accurately reflect

PQXNIH2- Protocol & Data and Safety Monitoring Plan

the neurological state of the patient can be readily extracted. PainQx personnel will also monitor the information collected via the ECRF to ensure that patient clinical information is being collected appropriately. Should any problems be identified, PainQx will communicate with the clinical site to address the issue.

Regulatory Issues

Reporting of Severe Adverse Event (SAE) and Adverse Event (AE)

An adverse event (AE) is the appearance or worsening of any undesirable sign, symptom, or medical condition occurring after starting the study even if the event is not considered to be related to the equipment used for the study. Medical conditions/diseases present before starting the study are only considered adverse events if they worsen after starting the study.

A serious adverse event (SAE) is defined as an event that:

- Is fatal or life-threatening
- Results in persistent or significant disability/incapacity
- Constitutes a congenital anomaly/birth defect
- Requires in-subject hospitalization or prolongation of existing hospitalization, unless hospitalization is for:
 - elective or pre-planned treatment for a pre-existing condition that is unrelated to the indication under study and has not worsened since the start of study test product
 - treatment on an emergency out-subject basis for an event not fulfilling any of the definitions of an SAE given above and not resulting in hospital admission
 - social reasons and respite care in the absence of any deterioration in the subject's general condition
- Is medically significant, i.e., defined as an event that jeopardizes the subject or may require medical or surgical intervention to prevent one of the outcomes listed above.

In the event of any SAE, AE and medical or health emergency, participants will be instructed to call 911 or other emergent care assistance and subsequently report the incident to the PainQx the principal investigator (**[name] [contact]**), PainQx will not be able to assist the participants with any medical emergencies that may occur during the study.

Reporting of IRB actions to NIDA

PainQx will report any IRB actions to [name], Program Manager at NIDA ([contact])

PQXNIH2- Protocol & Data and Safety Monitoring Plan

Report of changes or amendments to the protocol

PainQx will report any changes or amendments to the protocol to [name], Program Manager at NIDA ([contact])

Trial Stopping Rules

Study subjects may decide to withdraw from the research study without any penalty and for any reason. Study subjects may be considered withdrawn if they state an intention to withdraw or fail to participate. Although subjects are not required to provide a reason for withdrawal, they will be asked by the research staff about their decision. PainQx researchers also reserve the right to remove a study participant from the study at any time for any reason (e.g., non-compliance with study requirements, safety reasons).

Study subjects may also withdraw permission for the use and disclosure of any of their protected information for research but must do so in writing to the Principal Investigator at the address provided on the first page.

Disclosure of any Conflict of Interest in the DSM

PainQx does not have an existing conflict of interest in the DSM or the clinical trial.

Trial Safety

Risks

Although there is minimal risk in acquiring EEG from a subject, and EEG systems are standard, widely-used medical devices, there is a risk that the technology as deployed for support of the study will not function as anticipated. It will be explained to the participants that these technologies are still evolving and they may experience glitches or malfunctions during the study. There is a chance that patients may experience some slight discomfort during preparation for the EEG procedure (e.g., technician putting on the EEG cap, etc.). Patients may also feel uncomfortable wearing the EEG cap, ear clips, or ECG electrode below the right collarbone. However, patients will be reminded that they are only required to wear the equipment during preparation and for 15 minutes while physiological data is being collected. Additionally, participants may find some questions related to their chronic pain treatment/management to be sensitive. However, participants will be reminded that they do not need to answer any questions that they do not feel comfortable answering.

Benefits

There is clinical-site determined stipend to participate in this study and participants may also

PQXNIH2- Protocol & Data and Safety Monitoring Plan

indirectly benefit from the long-term results of this research, which may advance knowledge in the field of chronic pain measurement to help in the diagnosis and treatment of chronic pain.

Trial Efficacy

PainQx will be conducting interim analysis of the data as it is collected to optimize the performance of its algorithms.

DSM Plan Administration

The PI ([name]) and the PainQx Clinical Site Manager will track and ensure that the clinical protocol is adhered to and report any adverse events to the National Institute on Drug Abuse (NIDA) via ([contact]).

Subjects will be monitored by study staff at the clinical site for the entirety of the 90-minute single visit with no plans for follow-up. Subjects will be provided with study staff contact information during the informed consent process should they want or need to follow up after the testing is completed.

Frequency of DSM

Data will be reviewed monthly during the course of the trial

Protection of Confidentiality

The clinical sites will collect and provide the anonymized patient collected data to PainQx under conditions of strict confidentiality. A unique coded identifier will be assigned at intake to each patient by the site coordinator, and only this code is used as the subject identifier throughout the study. All data will be kept in password-protected files or locked file cabinets. Attention will be rigorously paid to patient confidentiality at all levels of data handling by all study staff. Data will be made available exclusively on a need-to-know basis. Data monitoring will be done quarterly by the Data Monitoring Committee throughout the grant period led by the PI ([name]).

PainQx will also not be collecting information on any vulnerable populations such as fetuses, neonates, pregnant women, children, prisoners, institutionalized individuals, or others who may be considered vulnerable.

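### NRS 0 occurs only in healthy normals and NRS 1-10 only in chronic-pain patients, so any pooled 0-10 relationship needs the slope among patients reported beside it

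*Protocol*

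**What the plan says.** The Protocol's Subjects section plans "Two hundred fifty (250) male and female pain patients with symptoms in excess of 3 months duration", and adds 50 healthy normal subjects. The reason given for the normals is: "The normal subjects are added to assure that the study spans the entire pain scale including those with an NRS of 0".

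Two criteria decide who can hold which score:

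- For patients, the list under Inclusion Criteria, Pain Patients reads: "Patients with NRS pain scores across the full range (1-10) at the time of testing".
- For normals, the list headed Normal (no-pain) Group reads in part: "Subjects will be included with no history of pain with a duration of greater than 3 months". The same criterion requires that they report no pain at testing or in the preceding 3 months.

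The Study Overview says that Phase I "produced a biomarker that scales with the intensity of chronic pain the patient is reporting" on the NRS, and the present study is meant to replicate that relationship on a portable device. Specific Aim 2 is to "Optimize the PainQx algorithm and demonstrate performance using the selected EEG recording device", and Trial Efficacy adds that "PainQx will be conducting interim analysis of the data as it is collected to optimize the performance of its algorithms". Each subject attends one visit (DSM Plan Administration). No analysis model is stated.

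**The concern.** As the criteria are written, the two groups do not overlap on the NRS. Every zero comes from someone without chronic pain, and every non-zero score comes from someone with it. With a single visit, no patient is planned to be seen at NRS 0. The Subjects section nonetheless introduces the normals as the zero end of the intensity scale rather than as a comparison group.

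Patients and normals can differ in EEG for reasons other than current intensity. Chronicity itself is one. Medication is another: analgesics for the patient's "pain condition will be allowed in the following categories: oral and transcutaneous narcotics", among other classes. If both groups are put on one NRS axis without a term for status, any such difference enters the slope. It can raise or lower it.

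At stake is how the result can be read. From a pooled correlation alone, a reader could not tell how much of it is the biomarker tracking intensity among patients and how much is the biomarker telling patients from normals. The algorithm is also to be optimized on this study's data. If the normals enter that step as zeros, it could favour features that separate the groups.

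**Working it through.** The Protocol gives no correlation, slope or power figure to reproduce, so this is an illustration.

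**From the Protocol:** 250 patients at NRS 1-10 and 50 normals at NRS 0, so the proportion of normals is p = 50/300 = 1/6 and p(1-p) = 0.1389.

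**Assumed:** residual biomarker SD 1; a status shift of d biomarker SD; patient NRS with mean m = 5.5 and either uniform on 1-10 (variance s² = 8.25) or SD 2.2 (s² = 4.84). Results are given as uniform / SD 2.2.

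**1. Share of NRS variance due to status.** Var(NRS) = p(1-p)m² + (1-p)s².
- Uniform: 4.20 + 6.88 = 11.08. SD 2.2: 4.20 + 4.03 = 8.23.
- Share = 4.20/11.08 = 38% / 4.20/8.23 = 51%, from one-sixth of the subjects.

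**2. Pooled r when the slope among patients is zero.** r = p(1-p)·m·d / sqrt(Var(NRS) × (1 + p(1-p)d²)).
- d = 0.5: 0.382/sqrt(11.08 × 1.035) = 0.113 / 0.382/sqrt(8.23 × 1.035) = 0.131.
- d = 0.2: 0.153/sqrt(11.08 × 1.006) = 0.046 / 0.153/sqrt(8.23 × 1.006) = 0.053.

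**3. Chance that this pooled r is significant** (two-sided 5%, Fisher z, n = 300): about 1 - Φ(1.96 - atanh(r) × sqrt(297)).
- d = 0.5: about 50% / 62%.
- d = 0.2: about 12% / 15%.
- In simulation (uniform and three bell-shaped NRS distributions, 4,000 runs per setting), the test restricted to the 250 patients stayed at 4.5% to 5.5% for every d from 0.2 to 1.0.

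**4. Effect on the pooled slope.** Shift = p(1-p)·m·d/Var(NRS).
- d = 0.5: 0.382/11.08 = 0.034 / 0.382/8.23 = 0.046 biomarker SD per NRS point, added or subtracted according to the sign of d.

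**5. Precision.** 95% CI half-width = 1.96/(sqrt(n) × SD of NRS).
- Pooled, n = 300: 1.96/(17.32 × 3.33) = 0.034 / 1.96/(17.32 × 2.87) = 0.039.
- Patients, n = 250: 1.96/(15.81 × 2.87) = 0.043 / 1.96/(15.81 × 2.2) = 0.056.

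**6. Pooled model with a patient/normal indicator.** All normals sit at NRS 0, so they carry no slope information once the indicator is in; the slope estimate equals the patients-only slope. The SE of the indicator is sqrt(1/250 + m²/(250s²) + 1/50) = 0.197 / 0.221. Detecting a shift with 80% power needs 2.80 × SE = 0.55 / 0.62 SD. A shift of 0.2 SD would be detected in about 17% / 15% of trials. A non-significant indicator is therefore weak evidence that there is no shift.

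**The case against.** The strongest reply is that this belongs in a statistical analysis plan. No sentence commits the study to a pooled model, and an unseen plan may already report the slope among patients. That stands against any claim of omission, and none is made here. It does not remove the point: the eligibility rules fix the separation, and the Protocol itself gives the normals the role of zero on the intensity scale.

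Second, contrasting pain with no pain is arguably part of the target. The Study Overview also says that EEG can detect changes when a patient is in pain, and it names a 0-10 scale. An indicator would absorb a true step, or curvature near zero, along with any nuisance difference. This stands, and it is why the pooled result should be kept.

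Third, the slope among patients is not free of confounding. Analgesic use may vary with pain intensity within that group. This stands too: restricting to patients removes the patient/normal shift only. Medication is recorded (Collection of Subject Self-Rating and Pain Scales), so it can be examined.

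Fourth, the shift is assumed and may be small. This is correct.

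A reader might go further and infer that the design cannot test the hypothesis, that a pooled correlation would be spurious, or that the intensity claim must stand or fall on the patients alone. The documents support none of these. The slope among patients is estimable, the size of the shift is unknown, and the modest shifts considered here could not alone produce a large pooled r. Making the patients-only slope the criterion would also cost power: if the relation is linear over 0-10 with no status shift, a slope with 80% power pooled has about 60% / 50% in patients alone.

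**Conclusion.** The point holds as a minor one. Status and NRS 0 coincide by eligibility, so a pooled 0-10 relationship combines two things that only the patient data can begin to separate. The structural part rests on the Protocol's own criteria. The size rests on assumption: the patient NRS distribution, the residual SD and above all the status shift are not in the document, and the algorithm is still to be optimized. Under the assumptions used, a 0.5 SD shift could matter to the reading of a weak pooled correlation, while a 0.2 SD shift would matter little. The slope meant throughout is the slope across the 250 patients; with one visit each there is no longitudinal slope within a person.

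**What to change.** Amend the sentence on the normals in the Subjects section, for example:

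> The normal subjects are enrolled to show biomarker output at NRS 0 and will be reported as a separate patient/normal contrast. The NRS slope among the 250 pain patients (NRS 1-10) will be reported with its 95% confidence interval beside any pooled 0-10 result.

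A linear pooled model with a patient/normal indicator gives the same slope estimate and may be used instead, provided the indicator is not dropped because its test is non-significant.

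The pooled result is kept and no new success criterion is imposed. Enrolment and data collection do not change. The cost is in reporting: the patients-only slope has the wider interval computed above, and the patients-only correlation may be lower than the pooled one. The change does not deal with confounding by analgesic use among patients, and the report should say so.

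### An uncited neutrality claim cannot justify leaving gender, culture and ethnicity uncontrolled in an algorithm still being tuned, and it does not reach medication, which the design ties to NRS

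*Protocol*

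**What the plan says.** Target Population Distribution (under Trial Management) describes a convenience sample from referring practices: "There are no plans to control for gender, but the convenience nature may impact gender balance of the sample". It adds: "It is expected that gender will be approximately 50-50 in this sample". The reason for not controlling follows: the QEEG methods and the brain regions of interest "have been determined to be culture, ethnic and gender neutral", from which the protocol concludes that it need not control these variables strictly. No data or reference is given.

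Three other parts of the protocol bear on this:

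- **The algorithm is not fixed.** Specific Aim 2 is to "Optimize the PainQx algorithm and demonstrate performance using the selected EEG recording device", and Trial Efficacy adds interim analyses to tune performance as data accrue. Equipment & EEG Acquisition provides BioSignal Group headsets for the first 100 participants and Zeto headsets afterwards.
- **Medication differs by group.** Allowed analgesics are "oral and transcutaneous narcotics, tricyclic antidepressants, SNRIs, anticonvulsants, non-steriodals, and corticosteroids". The 50 normal subjects supply the NRS 0 end of the scale and must have no chronic pain history and no pain within 3 months of testing.
- **The data exist.** The physician's form records "medication history, including present medications", and Data Entry Methods says that demographic and medication data go into the eCRF.

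**The concern.** The protocol takes a position and gives a reason for it, and the reason does not carry the position. Neutrality of EEG methods and brain regions is not neutrality of an algorithm's output. An algorithm tuned to NRS can use any EEG feature that moves with NRS in the sample at hand, whether pain, a drug or a subject characteristic produces that feature. A determination made before the tuning cannot vouch for what the tuning selects.

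Medication is the main worry. Anyone at NRS 0 in the normal group lacks a pain reason for analgesics, while patients at NRS 1-10 may be on several CNS-active classes. Drug use and NRS are therefore linked by design, even if drug use is unrelated to pain intensity among the patients.

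The Study Overview makes this study the beta for the FDA validation trial. A biomarker-NRS relationship that partly reflects drug use could be taken as replication here and then weaken in a validation sample with a different case mix.

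**Working it through.** **Inputs from the protocol.** 250 patients at NRS 1-10 and 50 normal subjects at NRS 0, 300 in all. Headsets: 100 BioSignal, 300 − 100 = 200 Zeto. The protocol gives no alpha, power, effect size or minimum sample size, so its 300 cannot be reproduced. For scale, the correlation detectable with 80% power at two-sided 5% is tanh[(1.960 + 0.842)/√(n − 3)], which is 0.161 for n = 300 and 0.176 for n = 250.

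**Step 1: scope of the waiver.** The sentence names culture, ethnicity and gender. Age and medication are not mentioned; they are unaddressed, not waived.

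**Step 2: formula.** With no true pain effect, a factor correlated a with NRS and b with the biomarker gives an expected crude correlation of a × b. At n = 250 the critical |r| is 0.124. By Fisher z:

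- a = 0.2, b = 0.3: r = 0.06, significant in about 16% of trials
- a = 0.3, b = 0.4: r = 0.12, about 47%
- a = 0.4, b = 0.5: r = 0.20, about 89%

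The values of a and b are assumptions.

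**Step 3: simulation of this design.** Assumptions: NRS uniform on 1-10 in patients; normals unmedicated; 30%, 50% or 70% of patients medicated; a biomarker shifted 0.5 or 1.0 SD by drug use and unaffected by pain; drug use either unrelated to NRS among patients or rising with it (log-odds 0.2 per point). There were 2,000 replicates per setting, and tests were two-sided at 5%. Six of the twelve settings:

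| Medicated | Drug use vs NRS in patients | Shift (SD) | Mean r, all 300 | Mean r, patients alone | Significant, crude | Significant, adjusted for drug use |
|---|---|---|---|---|---|---|
| 30% | unrelated | 0.5 | 0.032 | −0.003 | 7.9% | 4.0% |
| 50% | unrelated | 1.0 | 0.105 | 0.001 | 43.9% | 3.6% |
| 70% | unrelated | 1.0 | 0.145 | 0.001 | 71.5% | 4.5% |
| 30% | rising | 0.5 | 0.074 | 0.056 | 25.9% | 5.1% |
| 50% | rising | 1.0 | 0.192 | 0.123 | 91.8% | 5.4% |
| 70% | rising | 1.0 | 0.218 | 0.103 | 97.8% | 5.1% |

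Over all twelve, crude false significance is 8-72% (unrelated) and 26-98% (rising). After adjustment it is 4-6%.

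**Step 4: check of one row by hand (50%, rising, 1.0 SD).** The medicated share of all subjects is 0.5 × 250/300 = 0.417, with variance 0.417 × 0.583 = 0.243 and SD 0.493. Then b = 0.493/√(1 + 0.243) = 0.442. The simulated a is 0.434, and 0.434 × 0.442 = 0.192, which matches the table.

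**Step 5: what restriction to patients does.** It removes the spurious correlation when drug use is unrelated to NRS among patients. When drug use rises with NRS, r of about 0.06 to 0.12 remains. Restriction and adjustment therefore answer different questions, and both are needed.

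**Step 6: sex alone.** With a 0.5 SD sex effect unrelated to NRS within patients (4,000 replicates), false significance is 5% at 50/50 in both groups, 5% at 60% vs 50%, and 7% at 65% vs 40%, with mean r at most 0.03.

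**The case against.** The strongest reply is that the sentence stands in a section on who will be recruited, before the data and analysis section begins. Strict control there most naturally means recruitment balance, and a convenience sample without quotas is defensible. That stands for sampling. But the wording is not confined to sampling, and a reader could take it as the protocol's position on the analysis too.

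A reader might also infer that the protocol waives control of all subject characteristics, age and drugs included. It does not. Nor is the lack of an adjustment model in itself an error: covariates and subgroup estimates are commonly left to the SAP, which is not at hand. The exclusion criteria also restrict the population in several ways, and the power analysis text foresees subset analyses by etiology.

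The numbers are open to challenge as well. The effect sizes are not in the documents. The simulation treats success as p < 0.05 on a crude correlation, a criterion that the protocol does not state. Replication of the Phase I relationship, whose strength is not given, might demand far more than r = 0.2. And for sex, the one waived variable simulated, the effect is small unless sex is related to NRS among patients or strongly affects the biomarker. All of this stands and limits the claim.

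Finally, stronger pain may lead to stronger drugs. Drug class is then partly a marker of severity, and adjusting for it can remove genuine pain signal. That also stands, and it governs how the adjusted result should be read.

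**Conclusion.** The concern holds in limited form. The neutrality statement is unsupported in the protocol and cannot cover an algorithm that is tuned in this study on two headsets, so it should not serve as a ground for leaving gender, culture or ethnicity out of the analysis. Medication is the more serious exposure, because the NRS 0 group links it to the outcome scale by design.

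Under the stated assumptions, a biomarker that responds only to drug use gives a mean crude r of 0.03 to 0.22, which overlaps the 0.161 detectable with 300 subjects. So it could pass as a weak pain signal. A large observed correlation would be much harder to explain this way. The range assumes no medicated normals, one fully recorded drug indicator and a fixed biomarker; the effect of tuning is not modelled.

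A reader might conclude that the biomarker is in fact a drug, age or sex signal. The documents do not support that: they give no effect of any of these on the biomarker. This is a risk that the report should be able to rule out, and worth acting on because the remedy is cheap.

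**What to change.** 1. Under Target Population Distribution, cite evidence for the neutrality sentence or delete it, and say that the lack of strict control concerns recruitment only. Convenience sampling without quotas can stay.
2. Beside the crude biomarker-NRS relationship, report it adjusted for age, sex, CNS-active drug class (yes/no per class) and headset.
3. Report it also in the pain patients alone, and by sex and by race/ethnicity with confidence intervals.
4. State in advance that a weaker drug-adjusted figure is a sensitivity result and not proof of confounding, since drug class may partly reflect pain severity.
5. Before drug classes are coded, reconcile the exclusion of patients on anticonvulsants with the allowed list, which includes them.

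The cost is wording and a few model terms. Demographic and medication data are already collected, and headset follows from enrolment order. The protocol does not itemise the demographic fields, so confirm that race and ethnicity are among them. No change in recruitment or treatment is needed. The price is that the adjusted figure may be less favourable and that the race/ethnicity estimates will be imprecise if some groups are small.
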